In the double-blind phase of the pooled Phase 3 studies SUI3001/3002, SAEs were reported for 4.0% participants in the esketamine + SOC group (suicide attempt, depression suicidal, depersonalization/derealization disorder, depression, suicidal ideation, and diabetic ketoacidosis) and 5.3% participants in the placebo + SOC group (suicide attempt, depression suicidal, depression, suicidal ideation, aggression, arrhythmia, pericardial effusion, hypertransaminasemia, and pneumothorax). After discontinuation from the double-blind phase, 1.3% participants in the esketamine + SOC group experienced SAEs (suicidal ideation and acute psychosis) versus 0.9% participants in the placebo + SOC group (depression suicidal, major depression, and suicide attempt). During the follow-up phase, SAEs were observed at similar rates in participants who were treated with esketamine + SOC during the double-blind phase and participants who were treated with placebo + SOC during the double-blind phase (11.6% and 11.9%, respectively). In the Phase 2 study SUI2001, SAEs were observed in 11.4% participants in the esketamine + SOC group and 0 participants in the placebo + SOC group during the double-blind phase, and in 3.7% participants and 22.7% participants, respectively, during the follow-up phase.

Adverse Events Leading to Discontinuation

Across the 19 Phase 1 studies, TEAEs led to withdrawal of 18 participants from study treatment in studies TRD1018 (6 participants); TRD1013 (4 participants); TRD1001 (2 participants); TRD1004, TRD1006, TRD1007, TRD1009, TRD1015 and TRD1020 (1 participant each).

Participants with TRD

In the Phase 2 Study TRD2003, 4 participants experienced TEAEs which led to withdrawal of study medication: 3 participants due to at least 1 TEAEs of syncope, headache or dissociative disorder in double-blind phase and 1 participant due to an SAE of ectopic pregnancy in the open-label phase. Except for ectopic pregnancy, all other events were considered as possibly or very likely related to the study drug.

TEAEs leading to discontinuation of esketamine were reported in approximately 5% to 6% of participants in the Phase 3 short-term studies in both adult and elderly participants, although rates were higher than for the oral AD + placebo groups (pooled TRD3001/TRD3002: 4.6% [vs 1.4% for oral AD + placebo]; Study TRD3005: 5.6% [vs 3.1% for oral AD + placebo]).

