10.2. Appendix 2: Clinical Laboratory Tests

The following tests will be performed according to the Schedule of Activities by the central laboratory:

Protocol-Required Safety Laboratory Assessments

Laboratory Assessments	Parameters		
Hematology	Platelet count Red blood cell count Hemoglobin Hematocrit	RBC Indices: MCV MCH % Reticulocytes	White Blood Cell (WBC) count with Differential: Neutrophils Lymphocytes Monocytes Eosinophils Basophils
	Note: A WBC evaluation may include any abnormal cells, which will then be reported by the laboratory. A RBC evaluation may include abnormalities in the RBC count, RBC parameters, or RBC morphology, which will then be reported by the laboratory. In addition, any other abnormal cells in a blood smear will also be reported.		
Clinical Chemistry	Sodium Potassium Chloride Bicarbonate Blood urea nitrogen (BUN) Creatinine Glucose [fasting] Aspartate aminotransferase (AST)/Serum glutamic-oxaloacetic Alanine aminotransferase (ALT)/Serum glutamic-oxaloacetic Gamma-glutamyltransferase (GGT)	Total and Direct bilirubin Alkaline phosphatase Creatine phosphokinase (CPK) Lactic acid dehydrogenase (LDH) Uric acid Calcium Phosphate Albumin Total protein Magnesium	
	Note: All events of ALT $\geq 3 \times$ upper limit of normal (ULN) and bilirubin $\geq 2 \times$ ULN ($>35\%$ direct bilirubin) or ALT $\geq 3 \times$ ULN and international normalized ratio (INR) >1.5 , if INR measured which may indicate severe liver injury (possible Hy's Law), must be reported as a serious adverse event (excluding studies of hepatic impairment or cirrhosis).		
Routine Urinalysis	Dipstick Specific gravity pH Glucose Protein Blood Ketones Bilirubin Urobilinogen Nitrite Leukocyte esterase	Sediment (if dipstick result is abnormal) Red blood cells White blood cells Epithelial cells Crystals Casts Bacteria	
	If dipstick result is abnormal, flow cytometry will be used to measure sediment. In case of discordance between the dipstick results and the flow cytometric results, the sediment will be examined microscopically.		

Laboratory Assessments	Parameters
Other Screening Tests	
• Serum and Urine Pregnancy Testing for women of childbearing potential only• Urine Drug Screen opiates (including methadone), cocaine, MDMA amphetamines, methamphetamines, cannabinoids and barbiturates.• TSH• HbA1c

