10.4.5. Procedures

All Adverse Events

All adverse events, regardless of seriousness, severity, or presumed relationship to study intervention, must be recorded using medical terminology in the source document and the CRF. Whenever possible, diagnoses should be given when signs and symptoms are due to a common etiology (eg, cough, runny nose, sneezing, sore throat, and head congestion should be reported as "upper respiratory infection"). Investigators must record in the CRF their opinion concerning the relationship of the adverse event to study therapy. All measures required for adverse event management must be recorded in the source document and reported according to sponsor instructions.

For all studies with an outpatient phase, including open-label studies, the participant must be provided with a "wallet (study) card" and instructed to carry this card with them for the duration of the study indicating the following:

- Study number
- Statement, in the local language(s), that the participant is participating in a clinical study
- Investigator's name and 24-hour contact telephone number
- Local sponsor's name and 24-hour contact telephone number (for medical personnel only)
- Site number
- Participant number
- Any other information that is required to do an emergency breaking of the blind

Serious Adverse Events

All serious adverse events that have not resolved by the end of the study, or that have not resolved upon discontinuation of the participant's participation in the study, must be followed until any of the following occurs:

- The event resolves
- The event stabilizes
- The event returns to baseline, if a baseline value/status is available
- The event can be attributed to agents other than the study intervention or to factors unrelated to study conduct
- It becomes unlikely that any additional information can be obtained (participant or health care practitioner refusal to provide additional information, lost to follow-up after demonstration of due diligence with follow-up efforts)

Suspected transmission of an infectious agent by a medicinal product will be reported as a serious adverse event. Any event requiring hospitalization (or prolongation of hospitalization) that occurs during the course of a participant's participation in a study must be reported as a serious adverse event, except hospitalizations for the following:

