- For participants who discontinued double-blind treatment but continued to be assessed until the end of double-blind phase (Day 28), AEs will be considered as treatment-emergent for the double-blind phase only if they satisfy the condition: double-blind phase start date /time ≤ AE onset date/time ≤ last day of double-blind treatment.

Open-label treatment phase:

- For participants who received open-label esketamine nasal spray, all AEs that are assigned to the open-label treatment phase will be considered as treatment-emergent if they satisfy the condition: open label treatment phase start date/time≤ AE onset date/time ≤ open label treatment phase end date.
 - AEs that occur on the last day of double-blind phase but AE onset time is after open-label dosing will be considered as treatment-emergent for the open-label treatment phase.

Observation phase:

• For participants who received SOC only in the observation phase, all AEs that are assigned to the observation phase will not be considered as treatment-emergent if they satisfy the condition: double-blind phase end date+1≤ AE onset date ≤ observation phase end date.

Follow-up phase:

• Any AEs that are assigned to the follow-up phase will not be considered as treatmentemergent. AEs during the follow-up phase should satisfy the condition: follow-up phase start date ≤AE onset date ≤follow-up phase end date.

Summary tables will be provided for adverse events by phase:

- AEs
- Serious AEs (SAEs)
- AEs leading to discontinuation of each study agent within a study intervention
- AEs by severity
- AEs by relationship to each study agent within a study intervention
- AEs of special interest

In addition to the summary tables, listings will be provided for participants who had:

- SAEs
- AEs leading to discontinuation of study intervention
- AEs of special interest

Incidence of other treatment-emergent adverse events of special interest will be summarized. See Appendix 7 for list of adverse events in each category.

The proportion of TEAEs occurring on dosing days and the proportion of TEAEs that occur on dosing days with same day resolution will be summarized. Duration and resolution time of severe TEAEs will also be summarized.

A listing of participants who died will be provided.

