6.7. Appendix 7 Adverse Events of Special Interest

Adverse events of special interest are defined as follows:

AE Special Interest Category	Preferred Term
Drug abuse, dependence and withdrawal Increased blood pressure	Aggression, Confusional state, Decreased activity, Dependence, Disorientation, Dissociation, Dissociative disorder, Dizziness, Drug use disorder, Drug abuse, Drug abuser, Drug dependence, Drug detoxification, Drug diversion, Drug rehabilitation, Drug tolerance, Drug tolerance increased, Drug withdrawal convulsions, Drug withdrawal headache, Drug withdrawal syndrome, Euphoric mood, Feeling abnormal, Feeling drunk, Feeling of relaxation, Hallucination, Hallucination auditory, Hallucination gustatory, Hallucination olfactory, Hallucination synesthetic, Hallucination tactile, Hallucination visual, Hallucinations mixed, Inappropriate affect, Mental impairment, Product tampering, Psychomotor hyperactivity, Psychotic disorder, Rebound effect, Somatic Hallucination, Somnolence, Substance abuser, Substance dependence, Substance use, Substance use disorder, Substance-induced mood disorder, Substance-induced psychotic disorder, Thinking abnormal, Withdrawal arrhythmia, Withdrawal syndrome Blood pressure increased, Blood pressure diastolic increased, Blood
increased blood pressure	pressure systolic increased, Hypertensive crisis, Hypertensive emergency, Hypertension
Increased heart rate	Heart rate increased, Tachycardia, Extrasystoles
Transient dizziness/vertigo	Dizziness, Dizziness exertional, Dizziness postural, Dizziness procedural, Procedural dizziness, Vertigo, Vertigo labyrinthine, Vertigo positional, Vertigo CNS origin
Impaired cognition	Cognitive disorder
Cystitis	Allergic cystitis, Chemical cystitis, Cystitis, Cystitis erosive, Cystitis haemorrhagic, Cystitis interstitial, Cystitis noninfective, Cystitis ulcerative, Cystitis-like symptom, Pollakiuria, Dysuria, Micturition urgency, Nocturia
Anxiety	Anticipatory anxiety, Anxiety, Anxiety disorder, Agitation, Fear, Feeling jittery, Irritability, Nervousness, Panic attack, Tension
Anticipated Dosing-related AEs	Anxiety, Anticipatory anxiety, Dissociation, Dizziness, Dizziness postural, Feeling abnormal, Feeling drunk, Nausea, Somnolence, Vertigo, Vomiting

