Events potentially related to suicidality	Completed suicide, Depression suicidal, Intentional overdose, Intentional self-injury, Multiple drug overdose intentional, Poisoning deliberate, Self-injurious behavior, Self-injurious behaviour Self-injurious ideation, Suicidal behavior, Suicidal behaviour, Suicidal ideation, Suicidal attempt
Hepatic adverse events	Cholecystitis, Cholelithiasis, Hepatic steatosis, Hepatitis, Non-alcoholic steatohepatitis, Primary biliary cholangitis, Alanine aminotransferase increased, Aspartate aminotransferase increased, Blood bilirubin increased, Gamma-glutamyl transferase increased, Hepatic enzyme increased, Liver function test abnormal, Liver function test increased, Transaminases increased, Urine bilirubin increased, Urobilinogen urine increased
Events related to renal disorders	Cystitis, Pyelonephritis, Urethritis, Urinary tract infection, Blood creatinine increased, Blood urea increased, Blood urine present, Creatinine renal clearance increased, Protein urine present, Urine analysis abnormal, Urine leukocyte esterase positive, Bladder discomfort, Bladder irritation, Bladder outlet obstruction, Cystitis noninfective, Dysuria, Haematuria, Hypertonic bladder, Lower urinary tract symptoms, Micturition urgency, Nephrolithiasis, Nocturia, Pollakiuria, Polyuria, Proteinuria, Renal colic, Renal failure, Semenuria, Stress urinary incontinence, Ureterolithiasis, Urge incontinence, Urinary bladder polyp, Urinary hesitation, Urinary incontinence, Urinary retention

AE Special Interest Category	Preferred Term
Symptoms of dissociation	Dissociation[QX[2]
persisting beyond the typical ≤ 2	
hour post esketamine	
administration	
Delirium	Post-injection delirium sedation syndrome, Postoperative delirium,
	Delirium, Intensive care unit delirium
Psychosis	Acute psychosis, Affective disorder, Alcoholic psychosis, Bipolar I
	disorder, Epileptic psychosis, Hysterical psychosis, Mania, Parkinson's
	disease psychosis, Postictal psychosis, Psychosis postoperative, Psychotic
	disorder, Psychotic disorder due to a general medical condition, Reactive
	psychosis, Rebound psychosis, Schizoaffective disorder, Substance-
	induced psychotic disorder, Transient psychosis
Mania	Hypomania, Mania

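### The closed hepatic special-interest list has no term for liver injury, drug-induced liver injury, hepatic failure or jaundice, so an event coded only to one of these could be left out of the grouped hepatic count

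*SAP*

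**What the plan says.** SAP 6.7 (Appendix 7) introduces its table with "Adverse events of special interest are defined as follows" and then gives preferred terms by category. SAP 5.6.2 bases the special-interest incidence summary on that table: "See Appendix 7 for list of adverse events in each category". It also plans a listing of participants with special-interest events. Neither place mentions a broader search or a medical review that could add cases.

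The hepatic row begins "Cholecystitis, Cholelithiasis, Hepatic steatosis, Hepatitis, Non-alcoholic steatohepatitis, Primary biliary cholangitis, Alanine aminotransferase increased" and ends "Liver function test abnormal, Liver function test increased, Transaminases increased, Urine bilirubin increased, Urobilinogen urine increased".

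Three parts of the protocol bear on what might be reported:

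- **Section 10.2 (Appendix 2).** ALT of at least 3 times the upper limit of normal, together with bilirubin of at least 2 times that limit (more than 35% direct) or INR above 1.5 if measured, is an event "which may indicate severe liver injury (possible Hy's Law), must be reported as a serious adverse event".
- **Section 10.4.5.** Sites are told: "Whenever possible, diagnoses should be given when signs and symptoms are due to a common etiology".
- **Section 2.2.** The serious events in the placebo + SOC group of the pooled Phase 3 MDSI studies include "aggression, arrhythmia, pericardial effusion, hypertransaminasemia, and pneumothorax".

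**The concern.** The list defines the category, so the grouped count can be no better than the terms in it. A site that meets the Appendix 2 criteria and follows the advice to give a diagnosis may report one event, such as liver injury, and no separate enzyme event. No term in the row matches that event, whereas an isolated ALT rise does match.

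What is at stake is the accuracy of one descriptive safety output. Protocol 9.4.5 plans no laboratory analysis. The additional safety assessments in SAP 5.6.3 cover vital signs, physical findings and the C-SSRS. Neither document, as shown, describes a liver-chemistry or Hy's Law summary. The hepatic row is therefore the only place where liver events are grouped, and someone reading only that row could see zero while a liver SAE is tabulated under another term.

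**Working it through.** The plan gives no figure to reproduce for this point. The check is a count of the list and a comparison with the reporting rules.

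**1. Count of the hepatic row (SAP Appendix 7)**

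| Type | Terms | Number |
|---|---|---|
| Gallbladder | Cholecystitis, Cholelithiasis | 2 |
| Liver diagnoses | Hepatic steatosis, Hepatitis, Non-alcoholic steatohepatitis, Primary biliary cholangitis | 4 |
| Laboratory | ALT, AST, blood bilirubin, GGT and hepatic enzyme increased; liver function test abnormal; liver function test increased; transaminases, urine bilirubin and urobilinogen increased | 10 |
| **Total** | | **2 + 4 + 10 = 16** |

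Terms naming liver injury, drug-induced liver injury, hepatic failure or jaundice: 0. The renal row directly below does include Renal failure.

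**2. Whether one liver event is counted, by how it is recorded**

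| Recorded and coded as | Counted in the hepatic row? |
|---|---|
| ALT increased and blood bilirubin increased | Yes |
| Hepatitis | Yes |
| Liver injury plus a separate ALT event | Yes, through the ALT event |
| Liver injury, drug-induced liver injury, hepatic failure or jaundice alone | No |
| Hypertransaminasaemia alone | No, unless the dictionary maps it to a listed term |

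The gap is confined to the last two lines.

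**3. Where an uncounted event still appears**

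- If treatment-emergent, in the overall adverse event tables and the tables by severity and relationship (SAP 5.6.2).
- If it led to discontinuation, in that table and listing (SAP 5.6.2).
- If serious, in the SAE table and listing (SAP 5.6.2), and in a narrative (protocol 9.4.5).
- Not in the grouped hepatic incidence, nor in the special-interest listing.

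**4. Size of one missed case**

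The target is 446 randomized at 2:1:1. Assuming everyone randomized is dosed, an esketamine arm in the double-blind safety set has 446 × 1/4 = 111.5 participants. One case is 1/111 = 0.9%. If it is missed, the category shows 0.

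**The case against.** The case against giving this weight is strong, and most of it stands.

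- **The row is not blind to liver disease.** A reader might infer that it holds only laboratory and gallbladder terms. It names four liver diagnoses, and a severe event coded as Hepatitis is counted.
- **Omission is possible, not certain.** A reader might infer that an Appendix 2 liver SAE would necessarily be missed. The diagnosis instruction applies only where possible. The Appendix 2 event is triggered by laboratory values, and nothing requires it to be relabelled as liver injury. Protocol 8.2.4 has investigators record clinically relevant laboratory changes as adverse events, and the row contains the matching ALT and bilirubin terms.
- **No severity gradient is shown.** A reader might infer that the worse the event, the less likely it is to be counted. The documents say nothing on how sites or coders would term severe cases, and severe hepatitis or a marked enzyme and bilirubin rise reported as such is counted.
- **The liver note is not the protocol's only mandated SAE.** Abnormal pregnancy outcomes (8.3.5), suspected transmission of an infectious agent and the cause of a death within 30 days of the last dose (10.4.5) are also named.
- **The category is supplementary.** The protocol's special-interest categories (8.3.6 and 9.4.5) include no hepatic group, which the SAP adds. No endpoint or test uses it. Protocol 2.2 reports low rates of ALT/AST elevation and no case meeting Hy's law in any esketamine study.
- **The hypertransaminasaemia example is limited.** It arose in a placebo + SOC group, so it signals nothing about esketamine. Whether it codes apart from the listed term for increased transaminases depends on a MedDRA version the documents do not state.

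These points reduce the consequence but do not close the gap. The list is closed, the terms are absent, and no other grouped hepatic output is described. The sponsor has already made an edit of this kind: SAP version 4.0 added two spelling variants to the suicidality row to make the list more comprehensive.

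**Conclusion.** The concern holds in a limited form. The hepatic row could undercount the grouped hepatic incidence when an event is coded only to an unlisted liver term and no listed laboratory event accompanies it. The likely effect is none or a single case, about 0.9% of an esketamine arm. A serious case would remain visible elsewhere in the report, and no efficacy conclusion depends on the row.

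This rests on three assumptions: the list is applied by exact preferred term, as SAP Appendix 7 reads; the absent terms exist as separate preferred terms in the dictionary version used; and no liver-chemistry summary is planned outside the text shown. It is a free improvement and a nice-to-have, not a defect that threatens the trial's conclusions.

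**What to change.** Edit the hepatic row of SAP Appendix 7 in two ways:

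1. Add the preferred terms for liver injury, drug-induced liver injury, hepatic failure, jaundice and hypertransaminasaemia, with names and spellings checked against the MedDRA version in use.
2. State that any SAE reported under the ALT/bilirubin/INR note in protocol Appendix 2 counts in the hepatic category whatever its preferred term.

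The second change matters more, because it does not depend on anticipating every term a coder might choose. The cost is one row of one appendix and a small programming change, with no new data and no change to trial conduct.

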23. Participant is an employee of the investigator or study site, with direct involvement in the proposed study or other studies under the direction of that investigator or study site, as well as family members of the employees or the investigator.
24. Participant has severe renal impairment (creatinine clearance <30 mL/min).
25. Participant has not completed the mandatory 2-week antidepressant drug-free period prior to Day 1 of the double-blind treatment phase.

NOTE: Investigators should ensure that all study enrollment criteria have been met at screening and/or Day 1 prior to randomization (as applicable). If a participant's clinical status changes (including any available laboratory results or receipt of additional medical records) after screening but before the first dose of study intervention is given such that the participant no longer meets all eligibility criteria, then the participant should be excluded from participation in the study. Section 5.3, Screen Failures, describes options for retesting. The required source documentation to support meeting the enrollment criteria are noted in Section 10.3, Appendix 3, Regulatory, Ethical, and Study Oversight Considerations.

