9.4.5. Safety Analyses

Adverse Events

Safety data will be analyzed separately for each phase. Adverse events will be coded using the Medical Dictionary for Regulatory Activities (MedDRA). All reported adverse events with onset during the treatment phase (ie, treatment-emergent adverse events, and adverse events that have worsened since baseline) will be included in the analysis. For each adverse event, the percentage of participants who experience at least 1 occurrence of the given event will be summarized by treatment group.

Treatment emergent AEs of special interest will be examined separately grouped in the following categories: suggestive of abuse potential, increased blood pressure, increased heart rate, transient dizziness/vertigo, impaired cognition, cystitis, anxiety, and anticipated dosing-related AEs (See Section 8.3.6 for details).

Adverse events of special interest will be further listed in the SAP. Participants who discontinue treatment due to an adverse event and serious adverse events (SAEs) will be summarized separately. Narratives will be provided for deaths, SAEs, and participants who discontinue due to an AE.

Vital Signs

Descriptive statistics of temperature, pulse/heart rate, body weight measurements, and blood pressure (systolic and diastolic) values and changes from baseline will be summarized at each scheduled time point. The percentage of participants with values beyond clinically important limits will be summarized.

C-SSRS

A frequency distribution of C-SSRS scores at each scheduled timepoint by treatment will be provided. Shifts from the baseline visit to the most severe/maximum score during each study phase will be summarized by treatment. The maximum score assigned for each participant will also be summarized into one of three categories: no suicidal ideation or behavior (0), suicidal ideation (1-5), suicidal behavior (6-10).

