5.6.2. Adverse Events

The verbatim terms used in the CRF by investigators to identify adverse events will be coded using the Medical Dictionary for Regulatory Activities (MedDRA). Any AE occurring at or after the initial administration of study intervention through the day of last dose is considered to be treatment emergent. If the event occurs on the day of the initial administration of study intervention, and either event time or time of administration are missing, then the event will be assumed to be treatment emergent. If the event date is recorded as partial or completely missing, then the event will be considered to be treatment emergent unless it is known to be prior to the first administration of study intervention based on partial onset date or resolution date. All reported treatment-emergent adverse events will be included in the analysis. For each adverse event, the number and percentage of participants who experience at least 1 occurrence of the given event will be summarized by intervention group.

Assignment of adverse events to double-blind, open-label treatment/observation or follow-up phase will be made based on the following rules:

Double-blind phase:

AEs will be assigned to the double-blind analysis phase as detailed below.

- For participants who did not continue to open-label treatment/observation phase or participants who chose to be observed only (receive SOC only) in the observation phase: double-blind phase start date/time ≤AE onset date/time ≤double-blind phase end date.
- For participants who received open-label esketamine nasal spray: double-blind phase start date /time ≤AE onset date/time <double-blind phase end date/time (ie, open-label phase start date/time)
 - AEs that occur on the last day of double-blind phase but AE onset time is missing will be assigned to the double-blind phase.

AEs that are assigned to the double-blind analysis phase as detailed below will be considered as treatment-emergent.

- For participants completed double-blind treatment: all the AEs in the double-blind treatment phase will be considered as treatment-emergent for the double-blind phase.
- For participants who discontinued double-blind treatment and double-blind phase at the same time, all the AEs in the double-blind treatment phase will be considered as treatment-emergent for the double-blind phase.

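### The SAP renal special-interest list names increased but not decreased creatinine clearance, so an event coded only as decreased clearance falls outside that category

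*SAP*

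**What the plan says.** SAP Section 6.7 (Appendix 7) opens with "Adverse events of special interest are defined as follows" and gives a table of categories and preferred terms. The row for events related to renal disorders contains "Blood creatinine increased, Blood urea increased, Blood urine present, Creatinine renal clearance increased, Protein urine present" and, further on, "Proteinuria, Renal colic, Renal failure, Semenuria". SAP Section 5.6.2 plans an incidence summary and a participant listing for special-interest events, and settles category membership by reference: "See Appendix 7 for list of adverse events in each category".

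The protocol has no renal category among its special-interest events (Sections 8.3.6 and 9.4.5). It defers to the SAP: "Adverse events of special interest will be further listed in the SAP". Its one statement about the meaning of creatinine clearance is exclusion criterion 24 in Section 5.2: "Participant has severe renal impairment (creatinine clearance <30 mL/min".

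**The concern.** A preferred-term list is an operative definition: the program selects what is printed. In the protocol's own usage, low clearance is the adverse state. The two blood-chemistry terms just before it in the row, "Blood creatinine increased, Blood urea increased", also point to worse renal function. The clearance term points the other way, and neither document says why a rise would be of interest.

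At stake is the content of one descriptive safety category. An event coded only as decreased clearance would not enter the renal summary or listing, and an event coded as increased clearance would be reported there as a renal disorder.

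The list carries some extra weight because neither SAP Section 5.6 nor Protocol Section 9.4.5 plans a summary of clinical laboratory values. Protocol Section 8.2.4 asks the investigator to record clinically relevant laboratory changes as adverse events. Adverse event coding is therefore the planned route by which a renal laboratory change reaches the tables.

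**Working it through.** No arithmetic applies, and the plan states no figure to reproduce. The check is a reading of the list against the other sections.

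**Step 1: the renal row, term by term.** The row has 35 preferred terms.
- Terms about creatinine clearance: 1 of 35, and its direction is increased.
- Terms naming a decrease in clearance or filtration: 0 of 35.
- Terms that capture declining renal function by another name: 3 of 35 (Blood creatinine increased, Blood urea increased, Renal failure).

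**Step 2: the other Appendix 7 categories.** None contains a decreased-clearance or decreased-filtration term, so no other category picks the event up.

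**Step 3: the direction used elsewhere.** Exclusion criterion 24 sets severe impairment at clearance below 30 mL/min, so a fall is the adverse direction. With no renal category in the protocol, nothing there confirms or corrects the direction printed in the SAP.

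**Step 4: where each coding goes.** SAP Section 5.6.2 also states: "All reported treatment-emergent adverse events will be included in the analysis". For a treatment-emergent event:

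| Event coded as | Renal special-interest summary and listing | Overall TEAE tables |
|---|---|---|
| Blood creatinine increased | in | in |
| Blood urea increased | in | in |
| Renal failure | in | in |
| Decreased clearance only | **out** | in |
| Creatinine renal clearance increased | **in** | in |

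The last two rows are where the printed list and the protocol's usage part.

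**Step 5: how often it could matter.** The clinical chemistry panel in Protocol Appendix 2 includes creatinine and blood urea nitrogen but not creatinine clearance. A decline found by the study's own tests would more naturally be recorded as raised creatinine or urea, and both are listed. An event coded only as decreased clearance is therefore likely to be uncommon. The documents give no expected count.

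**The case against.** The strongest reply is that nothing important is lost. Three terms in the same row mark declining renal function, the scheduled laboratory tests lead towards two of them, and all treatment-emergent events are tabulated anyway. Serious events, events leading to discontinuation, severity and relationship are also tabulated without reference to this list. All of that stands. A reader might infer that the plan would miss falling renal function. The documents do not support that: only an event coded solely as decreased clearance leaves the category, and it leaves only the special-interest outputs.

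A second reply is that the direction cannot be proved wrong. The row is not presented as a list of declining function. It mixes infections, stones, incontinence, a bladder polyp and the non-directional Urine analysis abnormal, and no selection rule is given. This also stands in part. A reader might infer that the printed term is a proven slip that should simply be reversed. Criterion 24 shows what low clearance means, but it does not show how the list was built. The reply does not explain why a decrease is absent from a renal category that already includes raised creatinine, raised urea and renal failure.

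A third reply is that one term is too small to raise. However, the SAP version history shows that version 4.0 added two spelling variants to the suicidality category to make the term lists more complete. A one-term correction is in keeping with how the sponsor maintains this appendix.

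**Conclusion.** The point holds in a limited form. The renal row names increased clearance and omits decreased clearance, against the protocol's treatment of low clearance as impairment and without a stated reason. Followed as printed, it excludes an event coded only as decreased clearance and includes one coded as increased clearance.

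The size is minor: one term of 35, in one descriptive safety category, with few events likely to be affected. The primary and key secondary analyses, the multiplicity procedure and the sample size are not affected.

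The conclusion assumes that events are selected by the exact printed terms. The case for adding the decreased term is firm. The case for dropping the increased term depends on the sponsor's answer about what was intended.

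**What to change.** Before database lock, make two changes to the renal row of SAP Appendix 7:

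1. Add the preferred term for decreased creatinine clearance, with its exact wording taken from the MedDRA version used for coding.
2. Confirm the intended direction of Creatinine renal clearance increased. Remove it unless the SAP states why a rise is of interest; if it is kept, give that reason beside the list.

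The cost is a small SAP revision beyond version 4.0 and an update to the selection list used in programming. No new data collection is needed.
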